9.11. Interim Analyses

Two types of interim analyses will be performed:

- interim futility analyses, the aim of which is to discontinue the study if the efficacy of fexinidazole is markedly inferior to expectations, and
- an interim analysis of success, the aim of which is to accelerate the process for submission of the registration dossier if the efficacy of fexinidazole is superior to expectations. Unlike with usual interim analyses of success, this study will be continued to completion regardless of the result of the interim analysis in order to obtain a precise idea of the relapse rate and rate of intercurrent events in the long term.

Interim Futility Analyses

Futility analyses will be performed in order to inform decisions about possible study discontinuation, based on pre-determined stopping rules. The aim is to limit the number of patients exposed to the IP in the event that the latter should prove to have limited efficacy.

An independent statistician with no involvement in preparing the study, in the blind review of data or in the final statistical analyses will be responsible for performing the FAs. Based on the analyses, s/he will be able to recommend continuing the study or stopping it due to futility. The independent statistician will be the only person able to access the randomisation code at the time of the FAs.

No information concerning the magnitude of the treatment effect will be provided. The ISC/DSMB may use additional or more stringent rules to stop exposure to fexinidazole, particularly in the event of safety concerns. The ISC/DSMB may decide to disregard recommendations based on the FAs if death is not related to treatment failure, but to accident, crime, etc.

The FAs will be performed on raw data on the ITT population.

The FAs will be performed as soon as data are available at a given timepoint. However, since the size of the sample increases at each timepoint, additional analyses may be performed at the written request of the ISC/DSMB to improve the statistical power of the analyses (see Table 5 – Overview of Protocol-planned Futility Analyses, and Table 7 – Expected Enrolment Rate).

Information concerning statistical power, criteria and the rules for the FAs is presented in Table 5 – Overview of Protocol-planned Futility Analyses (p 107).

The quantitative thresholds for decisions provided in the table are correct if the actual sample size is equal to the planned sample size.

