Futility Analysis 1: EOT responder rate (n = 30). Performed if fewer than 27 out of 30 patients are responders at the EOT visit.

The 1st FA will be performed under certain conditions, once the outcome at the EOT visit is known for 30 patients, i.e. 20 patients exposed to fexinidazole and 10 patients exposed to NECT.

The blind will be lifted for the first 30 patients, and the analysis will be performed if and only if the number of responders is less than 27 out of 30 patients, based on the assumption that no deviations from randomised treatment assignment occur.

The study will be stopped if the actual percentage of responders in the fexinidazole group is significantly lower than 95%, which corresponds to the historical rate for melarsoprol at the end of treatment (published responder rate, p = 95.2%; n = 6840).

The test will be significant if the number of responders in the fexinidazole group is \leq 16 out of 20 patients.

Futility Analysis 2: EOT responder rate (n = 105). Performed if fewer than 98 out of 105 patients are responders at the EOT visit.

The 2nd FA will be performed under certain conditions, once the outcome at the EOT visit is known for 105 patients, i.e. 70 patients in the fexinidazole group and 35 patients in the NECT group.

The blind will be lifted for the first 105 patients, and the analysis will be performed if and only if the number of responders is less than 98 out of 105 patients.

The study will be stopped if:

 Rule 1: the actual percentage of responders in the fexinidazole group is significantly lower than 95%, which corresponds to the historical rate for melarsoprol at the end of treatment (published responder rate, p = 95.2%; n = 6840),

AND the percentage of responders in the NECT group is compatible with 99%.

The first test will be significant if the number of responders in the fexinidazole group is ≤ 62 out of 70 patients. The second condition will be met if the number of responders in the NECT group is ≥ 33 out of 35 patients.

 OR Rule 2: the percentage of responders in the NECT group is not compatible with 99%, AND the difference in the percentage of responders between fexinidazole and NECT is significantly higher than 4%, which corresponds to the historical difference at the end of treatment between melarsoprol and eflornithine (δ = 4%) (see Table 5 – Overview of Protocol-planned Futility Analyses; p 107).

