The test for comparison of the difference between the rates with a margin of 4% will be performed using a modified Blackwelder test, i.e. difference greater than the margin instead of smaller than the margin.

Futility Analysis 3: responder rate 3 months after the EOT (n = 105). Performed if fewer than 94 out of 105 patients are responders at 3 months.

The 3rd FA will be performed under certain conditions, once 105 patients have performed the 3-month visit.

The blind will be lifted for the first 105 patients, and the analysis will be performed if and only if the number of responders is less than 94 out of 105 patients at 3 months.

The study will be stopped if:

 Rule 1: the actual percentage of responders in the fexinidazole group is significantly lower than 91%, which corresponds to the historical rate for melarsoprol at 3 months (see Table 5 – Overview of Protocol-planned Futility Analyses; p 107);

AND the actual percentage of responders in the NECT group is compatible with 99%.

The first test will be significant if the number of responders in the fexinidazole group is \leq 59 out of 70 patients. The second condition will be met if the number of responders in the NECT group is \geq 33 out of 35 patients.

OR Rule 2: the percentage of responders in the NECT group is not compatible with 99%,
 AND the difference in the percentage of responders between fexinidazole and NECT is significantly higher than 7%, which corresponds to the rounded historical difference between melarsoprol and effornithine at 3 months (see Table 5 – Overview of Protocol-planned Futility Analyses; p

107).

Futility Analysis 4: responder rate 6 months after the EOT (n = 105). Performed if fewer than 84 out of 105 patients have a favourable outcome at 6 months.

The 4th FA will be performed under certain conditions, once 105 patients have performed the 6-month visit.

The blind will be lifted for the first 105 patients, and the analysis will be performed if and only if the number of responders at 6 months is less than 84 out of 105 patients.

The study will be stopped if:

• Rule 1: the actual percentage of responders in the fexinidazole group is significantly lower than 80%, which corresponds to the historical rate for melarsoprol at 6 months,

AND the percentage of responders in the NECT group is compatible with 95%.

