The first test will be significant if the number of responders in the fexinidazole group is \leq 49 out of 70 patients. The second condition will be met if the number of responders in the NECT group is \geq 30 out of 35 patients.

 OR Rule 2: the actual percentage of responders in the NECT group is not compatible with 95%,
 AND the difference in the percentage of responders between favinidezels.

AND the difference in the percentage of responders between fexinidazole and NECT ($p_{NECT} - p_{fexi}$) is significantly higher than 12%.

The 95% rate of favourable outcomes for NECT is lower than the historical rate (42), and slightly higher than the historical rate with effornithine. The 12% threshold corresponds to the rounded difference between the rate for effornithine and the rate for melarsoprol (see Table 5 -Overview of Protocol-planned Futility Analyses; p 107).

Futility Analysis 5: Favourable outcome rate at 12 months after EOT (n = 105). Performed if fewer than 80 out of 105 patients have a favourable outcome at 12 months.

The 5th FA will be performed under certain conditions, once 105 patients have performed the 12-month visit.

The blind will be lifted for the first 105 patients, and the analysis will be performed if and only if the number of responders at 12 months is less than 80 out of 105 patients.

The study will be stopped if:

• Rule 1: the actual percentage of responders in the fexinidazole group is significantly lower than 75%, which corresponds to the historical rate for melarsoprol at 12 months,

AND the percentage of responders in the NECT group is compatible with 95%.

The first test will be significant if the number of responders in the fexinidazole group is \leq 44 out of 70 patients. The second condition will be met if the number of responders in the NECT group is \geq 30 out of 35 patients;

OR Rule 2: the percentage of responders in the NECT group is not compatible with 95%,
 AND the difference in the percentage of responders between fexinidazole and NECT (p_{NECT} – p_{fexi}) is significantly higher than 13%.

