Treatment-related serious adverse events			x	x	x	x	х	x	х	x	x	x	х	x	x	x (up to 24 months)
Recording of concomitant medication	x	х	х	х	х	х	х	х	х	х	х	х	х	х	х	
Dry blood spot sampling										x D8 H3.15	x D9H3	x D10H3 D10H7.15	x D10H24	x D10H48		
CSF sampling													x D10H24			

Table 5 – Overview of Protocol-planned Analyses

Analysis	Patients (n) (ITT)	Timepoint	Efficacy endpoints	Stopping Rules \blacklozenge π : actual responder rate p: observed responder rate	Power Chances of stopping the study due to actual responder rate (exact power)	Chances of stopping the study unduly (exact probabilities)
Futility analysis 1 Performed if the number of responders is ≤ 26/30 patients	20 (fexi) 10 (NECT)	End-of- Treatment Visit	Responder = no evidence of trypanosomes* at end of treatment	Unacceptable limit: π fexi < 95% = worse than melarsoprol (published results on responder rate at end of treatment p= 95.2% for melarsoprol; n= 6840) Stop if p fexi ≤ 80% Or if the number of responders is ≤16 out of 20 patients	58.9% if π fexi = 80% 77.5% if π fexi = 75% 89.3% if π fexi = 70%	1.59% if π fexi = 95% 0.0043% if π fexi = π NECT = 99%
Futility analysis 2 Performed if the number of responders is ≤ 97/105 patients	70 (fexi) 35(NECT)	End-of- Treatment Visit	Responder = no evidence of trypanosomes* at end of treatment	Unacceptable limit: π fexi < 95% (historical responder rate for melarsoprol) with π NECT \ge 99% (expectation for NECT and eflornithine) Or if the difference between the responder rates is > 4% in favour of NECT: $\pi_{NECT} - \pi_{Fexi} > 4\%$ Stop if Rule 1: p fexi $\le 88.57\%$ ($\le 62/70$) and p NECT $\ge 94.29\%$ ($\ge 33/35$) OR Rule 2: p NECT - p Fexi $\ge 15.7\%$ and p NECT $< 94.2\%$ ($< 33/35$) (Rule 2: modified Blackwelder test)	Rule 1 40.1% if π fexi = 90% 84.3% if π fexi = 85% 98.0% if π fexi = 80% Rule 2 29% if π fexi = 85% and π NECT = 98% 63.2% if π fexi = 80% and π NECT = 98%	Rule 1 2.33% if π fexi = 95% 0.0000% (if π fexi = 99%) Rule 2 0.08% (if π fexi = 95% and π NECT = 98%) 0.02% (if π fexi = 95% and π NECT = 97%) Note: the probability of applying Rule 2 is low (0.5%) if NECT \approx efformithine

Analysis	Patients (n) (ITT)	Timepoint	Efficacy endpoints	Stopping Rules \blacklozenge π : actual responder rate p: observed responder rate	Power Chances of stopping the study due to actual responder rate (exact power)	Chances of stopping the study unduly (exact probabilities)

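### The Rule 2 difference cut-offs in Table 5 are critical values for a NECT arm with 34 or 35 responders out of 35, where Rule 2 cannot apply

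*Protocol*

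**What the plan says.** FA2 to FA5 each use "70 patients in the fexinidazole group and 35 patients in the NECT group". Rule 1 applies when the NECT count is compatible with its expected rate: at least 33/35 in FA2 and FA3, at least 30/35 in FA4 and FA5. Rule 2 takes over below those counts and adds a test on the difference. For FA2 the comparison with the 4% margin "will be performed using a modified Blackwelder test, i.e. difference greater than the margin instead of smaller than the margin". For FA3 the study stops if the difference between fexinidazole "and NECT is significantly higher than 7%, which corresponds to the rounded historical difference between melarsoprol and effornithine at 3 months". For FA5 the margin is 13%.

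Appendix 4, Table 5 turns each test into one observed difference, combined with the NECT condition: 15.7% with NECT below 33/35 (FA2, labelled "Rule 2: modified Blackwelder test"), 18.57% with NECT below 33/35 (FA3) and 25.71% with NECT below 30/35 (FA5). The table footnote repeats that the difference must be significantly above the margin. Section 9.11 states: "The quantitative thresholds for decisions provided in the table are correct if the actual sample size is equal to the planned sample size".

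**The concern.** The critical value of a two-sample test against a margin depends on the observed rates, because the variance does. A NECT arm at or near 100% contributes almost no variance, so a small difference reaches significance. Rule 2 excludes that situation by construction. Once NECT is low enough for Rule 2 to apply, the standard error is larger and the critical difference must be larger too. A single percentage per analysis cannot represent the test, and the ones printed are too small.

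At stake is a futility recommendation in a pivotal trial. For the same data the text says continue and the table says stop. The direction is always towards stopping on a difference not shown to exceed the margin. The committee is not told the size of the effect, so it may not notice.

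**Working it through.** **Inputs.** 70 fexinidazole and 35 NECT patients; margins 4%, 7%, 13%; Rule 2 region NECT ≤32/35 (FA2, FA3) and ≤29/35 (FA5) (section 9.11); cut-offs 11/70 = 15.71%, 13/70 = 18.57%, 18/70 = 25.71% (Table 5).

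**Alpha.** Not printed for the futility analyses. One-sided 0.025 is the level in section 9.1. It also fits Table 5's Rule 1 limits: 16/20 against 95% has exact size 1.59%, 62/70 against 95% has 2.33%, 58/70 against 91% has 2.2%, and 44/70 against 75% has 1.6% (45/70 would be 3.0%).

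**Test.** z = (pN − pF − margin − c) / √[pN(1−pN)/35 + pF(1−pF)/70], significant if z > 1.96. Here c = 0 (uncorrected) or c = 0.5(1/35 + 1/70) = 0.0214 (continuity-corrected). All pairs of counts were enumerated.

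**Reproducing the printed figures.** FA2 at NECT 35/35, corrected:
- fexinidazole 59/70: difference 0.1571, SE 0.0435, z = 0.0957/0.0435 = 2.20, significant;
- fexinidazole 60/70: difference 0.1429, SE 0.0418, z = 0.0814/0.0418 = 1.95, not significant.

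The critical difference is therefore 15.71%, as printed. The same calculation gives 18.57% for FA3 and 25.71% for FA5. Uncorrected, the same three values arise at NECT 34/35. The corrected test with no condition on the NECT count also gives Table 5's Rule 2 powers:

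| | True fexi / NECT | Printed power | Corrected test, no NECT condition | Table 5 rule with its NECT condition |
|---|---|---|---|---|
| FA2 | 85% / 98% | 29% | 29.6% | 0.08% |
| FA2 | 80% / 98% | 63.2% | 63.3% | 0.66% |
| FA3 | 85% / 98% | 13.1% | 13.1% | 0.02% |
| FA3 | 80% / 98% | 41.3% | 41.3% | 0.27% |
| FA5 | 70% / 95% | 33.4% | 33.4% | 0.01% |
| FA5 | 65% / 95% | 58.8% | 58.8% | 0.07% |

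**Inside the Rule 2 region.** FA2 at its cut-off with the highest NECT count allowed, 32/35 against 53/70: difference 0.9143 − 0.7571 = 0.1571; SE = √(0.002239 + 0.002627) = 0.0698; z = (0.1571 − 0.04)/0.0698 = 1.68. Corrected, z = (0.1571 − 0.04 − 0.0214)/0.0698 = 1.37. All three analyses (uncorrected / corrected):

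| | Counts at the cut-off | z | One-sided p | Printed cut-off | Critical difference at this NECT count |
|---|---|---|---|---|---|
| FA2 | 32/35 vs 53/70 | 1.68 / 1.37 | 0.047 / 0.085 | 15.7% | 18.6% / 21.4% |
| FA3 | 32/35 vs 51/70 | 1.63 / 1.33 | 0.052 / 0.093 | 18.57% | 21.4% / 24.3% |
| FA5 | 29/35 vs 40/70 | 1.46 / 1.22 | 0.072 / 0.112 | 25.71% | 31.4% / 32.9% |

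The pooled totals are 85, 83 and 69 of 105. All are below the triggers of 97, 93 and 79, so the analysis would be run and the table would say stop. At lower NECT counts z at the cut-off falls further (FA2 at 30/35: 1.45; FA5 at 27/35: 1.37).

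**Chance of a Rule 2 stop** under assumed true rates:

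| | True NECT / fexi | Table | Uncorrected test | Corrected test |
|---|---|---|---|---|
| FA2 | 90% / 80% | 7.4% | 2.4% | 0.8% |
| FA3 | 90% / 75% | 14.1% | 5.7% | 2.3% |
| FA5 | 85% / 60% | 9.1% | 2.0% | 1.2% |

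With the true difference equal to the margin and NECT truly 80%, table against uncorrected test gives 8.0% vs 2.4% (FA2), 8.7% vs 2.7% (FA3) and 1.3% vs 0.1% (FA5).

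**The case against.** The strongest reply is that this hardly matters.

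- **Rule 2 is rarely reached.** Table 5 puts the chance at 0.5% if NECT behaves like eflornithine, and P(NECT ≤32/35) at a true 99% is indeed 0.52%. At the planning rates of 94% and 89% (18-month figures, used only for illustration) the table's Rule 2 stop probability is about 0.03% in FA2 and smaller in FA3 and FA5. This stands.
- **Fexinidazole is already poor in the disputed outcomes.** Where table and test disagree it has at most 53, 51 or 40 of 70 responders, below the Rule 1 limits of 62, 59 and 44 in section 9.11. These would not be stops of a drug performing as hoped. This stands as to harm. But the protocol chose to judge fexinidazole against NECT when NECT underperforms, and the table does not implement that choice.
- **The text names the test, and the committee decides.** A statistician following the text would get the right answer. But the table says when to stop, and section 9.11 vouches for its thresholds, so two instructions remain in force.
- **Alpha is inferred.** The FA3 text gives a Rule 1 limit of 59/70, whose exact size against 91% is 4.8%, so 0.05 cannot be wholly excluded. At one-sided 0.05, uncorrected, only FA2 at exactly 32/35 becomes significant; FA3 and FA5 still fail.
- **The origin of the cut-offs is not fully settled.** The corrected test gives undue-stop risks of 0.034% (FA2) and 0.002% (FA3) at 95%/98%, where 0.08% and 0.02% are printed. The conclusion does not depend on the origin, only on the p-values at the cut-offs.
- **The looks may be over.** Table 7 reports 357 patients enrolled by the end of 2014 and each look uses 105, so the change may now be one of record. That is an inference; no dates are given.

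**Conclusion.** The printed Rule 2 cut-offs for FA2, FA3 and FA5 are wrong for the rule they belong to, and the sentence vouching for them is false. Against the uncorrected test they are too small by about 3 percentage points in FA2 and FA3 (18.57 − 15.71 = 2.86; 21.43 − 18.57 = 2.86) and about 6 in FA5 (31.43 − 25.71 = 5.72). Against the corrected test the shortfalls are about 6, 6 and 7 points. The Rule 2 powers beside them have the same cause: they leave out the NECT condition and overstate the power of the printed rule by a wide margin.

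This rests on one-sided 0.025 and on the unpooled Blackwelder statistic. Pooled and restricted-likelihood variances do not rescue the cut-offs. The consequence is limited to a trial in which NECT performs clearly below expectation. FA4's Rule 2 cut-off is not legible in the available text and is not judged.

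**What to change.** In Table 5, replace the single Rule 2 difference by the test itself (modified Blackwelder, with its one-sided level stated), or by critical pairs for the NECT counts where Rule 2 applies. State whether the continuity correction is used; the printed powers point to the corrected form. At one-sided 0.025, stop if the number of fexinidazole responders out of 70 is at most:

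| | NECT count | Uncorrected | Corrected |
|---|---|---|---|
| FA2 | 32/35 | 51 | 49 |
| FA2 | 31/35 | 48 | 47 |
| FA3 | 32/35 | 49 | 47 |
| FA3 | 31/35 | 46 | 44 |
| FA5 | 29/35 | 36 | 35 |
| FA5 | 28/35 | 34 | 33 |

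Extend the list to lower NECT counts, recheck FA4 in the same way, and recompute the Rule 2 powers with the NECT condition included. Delete or correct the sentence in section 9.11 on the thresholds. If the looks have already taken place, record which version was applied.

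The cost is a short recalculation and edits to one table and one sentence. No patients or data change. Rule 2 becomes harder to trigger than the printed cut-offs suggest.

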11.1. Investigator Site File

The Investigator's Site File must contain the protocol and protocol amendments, Independent Ethics Committee (IEC) and regulatory approval with all correspondence, a copy of the patient information and informed consent form, drug accountability records and curriculum vitae for study personnel, as well as authorisation forms and any other relevant documents or correspondence.

11.2. Case Report Forms

Data will be collected by laboratory technicians, physicians, nursing staff or caregivers authorised by the Investigator. Data collection will be supervised by the Investigator. Study-specific information will be entered in an electronic Case Report Form (e-CRF). Data generated from this information must be consistent with the source documents and any discrepancies must be explained. All data that are recorded directly in the e-CRF must be rendered anonymous, i.e. such that they can only be identified by the patient's code.

The Investigator must ensure the accuracy, completeness, legibility and timely entry of all data reported to the Sponsor via the e-CRF, and any other additional information that is requested. The Investigator is responsible for ensuring that all informed consent forms, screening forms and results of randomisation for all patients are stored in a secure location. Data will be entered in the e-CRF, saved and sent by Internet after each visit. The e-CRF will be signed electronically by the Investigator at the time of the interim analysis and at the end of the study, prior to closing the database.

11.3. Source Documents

The data in the e-CRF must be verified by direct inspection of the source documents. The source documents are the patient's medical files, the physicians' and nursing staff's notes, appointment books, originals of laboratory test results, ECG tracings, reports on specific assessments, signed informed consent forms, and patient screening/enrolment logs.

The Investigator must keep the source documents up to date, i.e. reports on laboratory tests and consultations, records of medical history and physical examination reports, so that they can be examined and/or audited by DND*i* or its designated clinical monitors and/or by the Regulatory Authorities.

11.4. Retention of Documents

The Investigator must retain all essential documents for at least two years after approval of the last marketing authorisation is obtained, and until there are no ongoing or planned applications for marketing authorisation, or until at least 15 years after the official stop date of clinical development of the study treatment. However, study documents may need to be retained for a longer period of time if required by local regulations in effect or by agreement with DND*i*. It is the responsibility of the Sponsor to inform the Investigator/institution as to when these documents no longer need to be retained. After that date, the documents may be destroyed with prior permission from DND*i*, subject to local regulations.

DND*i* must be notified in advance if the Investigator plans to assign the study records to another party or move them to another site.

11.5. Monitoring

Clinical monitors will perform regular monitoring visits during which they will verify source data, Informed Consent Forms, medical records, laboratory results, imaging reports, e-CRFs, drug dispensing logs and protocol violations. The monitors will be given access to the corresponding source documents for each patient on condition that that the patient's confidentiality is maintained in accordance with local regulations.

Monitoring visits at the investigational sites will be performed periodically by *DNDi* representatives or designated clinical monitors to ensure compliance with Good Clinical Practice and all aspects of the protocol. Source documents will be reviewed for verification of consistency with the data in the e-CRFs. It will be the clinical monitor's responsibility to inspect the e-CRFs at regular intervals. The Investigator will ensure that DND*i* designated representatives have direct access to source documents. It is important that the Investigators and the personnel concerned are available during monitoring visits. The Investigator agrees to cooperate with the clinical monitor to ensure that any problems detected during monitoring visits are resolved.

The monitoring visits provide DND*i* with the opportunity to assess progress of the study, to verify the accuracy and completeness of the e-CRFs and to resolve any inconsistencies in the study records, as well as to ensure compliance with all protocol requirements, applicable regulations and Investigator obligations.

Four types of visit are planned: site evaluation visit, site initiation visit, monitoring visit and site closure visit.

